Objective: To examine the effect of transfusion strategies on the components of the primary endpoint.

Hypotheses: A smaller proportion of participants receiving blood under a liberal transfusion strategy will experience post-randomization death from any cause, MI, coronary revascularization, acute renal failure, or post-randomization stroke, compared to participants under restrictive transfusion strategy at 90 days after randomization.

V. STUDY OUTCOME MEASURES

A. Primary Outcome

The primary outcome is defined as a composite endpoint of all-cause post-randomization mortality, myocardial infarction (MI), coronary revascularization, acute renal failure, or post-randomization ischemic stroke up to 90 days after randomization.

MI will be defined using the Third Universal Definition of Myocardial Infarction.³⁴ (Please see Appendix I.)

Acute renal failure will be defined as Acute Kidney Injury stage III according to RIFLE criteria: Serum creatinine rise greater than 3 times that of baseline creatinine; or if baseline serum creatinine is greater than 4 mg/dl, then rise more than 0.5 mg/dl compared to baseline; or urine output less than 0.3ml/Kg/hr for 24 hours; or anuria for 12 hours. Baseline creatinine will be considered the creatinine upon admission prior to the index operation. The above urine output criteria will be only used for patients who are in the ICU and have precise monitoring of their urinary output. For patients on the surgical floor only serum creatinine changes will be used for assessment of this endpoint.

Coronary revascularization will be defined as a coronary artery bypass graft, or percutaneous coronary intervention (either angioplasty or stenting).

Stroke will be defined as new unilateral neurological deficit that lasts for more than 24 hours, and is confirmed by a brain imaging modality (either computed tomography or magnetic resonance imaging study) demonstrating new brain infarct.

B. Secondary Outcomes

Outcome 1: A composite endpoint of post-randomization infectious complications at 90 days post-randomization: Infectious complications will include wound infections, pneumonia, and sepsis.

Wound infection will be defined according to the Centers for Disease Control and Prevention (CDC) guidelines as a) positive wound culture, or b) drainage of pus from a wound, or c) suspicion of wound infection that was drained operatively.

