Clinical Data: The site coordinator will also collect clinical data using information from the medical record and consult with the surgeon as needed. These will include height, weight, last preoperative serum Hb, albumin, blood pressure, and history of comorbidities, including coronary artery disease, end-stage renal disease, chronic obstructive pulmonary disease, hyperlipidemia, diabetes mellitus, and hypertension.

To assure that MI or acute renal failure have not occurred prior to the time of randomization the patient's chart will be reviewed for Troponin, EKG, and serum creatinine. If these values are available in the 24 hrs. prior to randomization, they will not be collected again. If unavailable within this period, EKG, serum creatinine, and troponin data will be collected within 24 hours from the time of randomization. If available at the institution, CK-MB will also be collected (not required).

We will also collect information on prior history of MI, coronary artery bypass, and stent placement. Furthermore, intraoperative assessments will be collected during the surgical procedure, such as type of operation, amount of intraoperative blood loss, intraoperative transfusion, amount and type of fluids administered, and length of the operation.

Lab, transfusion, EKG ordering procedures: Once the participant is randomized, a study team member should enter a CPRS note indicating (1) randomization arm, (2) lab/EKG collection schedule, and (3) transfusion regimen. When possible, the lab, EKG, and transfusion orders should be placed by a study team member. If verbal lab or transfusion orders are given by the

LSI to a resident or nurse, the order should be co-signed by the LSI according to the local facility's standard operating procedure. If the co-sign option is unavailable under Orders, the LSI or study team member must enter a CPRS note after the order has been placed indicating that the order was placed by resident/nurse at the LSI's request. If the note is entered by a study team member, the note must be co-signed by the LSI.

2. Follow-up Assessment

Follow-up assessments will be collected after participants are discharged from the hospital including 30- day and 90-day active follow-up assessments and one-year passive follow-up assessment.

a) Thirty Day Follow-up

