Participant Hb, creatinine, and troponin levels will be collected on days 1, 2, 3, 4, and 7 post-randomization or discharge (whatever is shortest). EKG will be performed on days 1 and 4 after randomization. If a participant is discharged prior to post-randomization day 4, EKG will be obtained at discharge. Results on Hb (standard of care/per transfusion protocol requirements), creatinine, troponin, and EKG performed at other time points will also be collected until discharge as supporting documentation for endpoint adjudication. If available at the institution, CK-MB will also be collected (not required).

Urine output will also be monitored in patients admitted to the Intensive Care Unit and it will be reviewed daily by the Study Coordinator. If the patient has anuria for more than 12 hours, or has urine output less than 0.3 ml/Kg/hr for more than 24 hours then the urine output will be documented as evidence for the development of ARF.

Hemoglobin and transfusion record: We will record the number of blood transfusions during the preoperative, intraoperative, and postoperative time periods. The protocol requires that Hb levels be measured on day of randomization, days 1,2,3, and 4 after randomization as well as on day 7 if the participant remains in the hospital. Hb measurements, performed as standard clinical practice, will also be recorded. The Site Coordinator will record information on a) preoperative, intra-operative, and postoperative transfusions, and b) Pre- and post-randomization Hb levels. Information on Hb levels and transfusions will be obtained by contacting the hospital laboratory directly or from the chart. Information on transfusions will be obtained from the chart and the blood bank.

XI. MONITORING AND REPORTING SERIOUS ADVERSE EVENTS

A. Importance of Serious Adverse Event Reporting

Timely and complete reporting of safety information assists study management in identifying any untoward medical occurrence, thereby allowing: a) protection of safety of study participants, b) a greater understanding of the overall safety profile of the study treatments and therapeutic modalities, c) improvements in study design or procedures, and d) compliance with regulatory requirements.

B. Role of the Local Site Investigator in Serious Adverse Event Monitoring

The local site investigator, as well as other site personnel, shall be personally responsible for the following requirements:

1. Closely monitoring all study participants for new SAEs;

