6.5. Medical History

The number and percentage of participants reporting a medical history will be summarized by the following medical conditions: Hypertension, hyperlipidemia, coronary artery disease, congestive heart failure, COPD or previous active TB, dementia or current change in mental status, MI within 6 months, malnourished or cachectic, cancer or current chemotherapy, immunodeficiency or infection with HIV, ischemic stroke or TIA, prior coronary stent, cardiac arrhythmias, MI older than 6 months, end stage renal disease, prior coronary bypass, diabetes treated with medications (oral hypoglycemic or insulin), past smoking, and current smoking (Tables 12a-b).

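### The acute renal failure component has no exception for participants already on chronic dialysis, so it can score a chronic state as a primary-endpoint event; the resulting dilution is of unknown but probably modest size.

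*Protocol*

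**What the plan says.** The ARF definition is the same in Protocol V.A and SAP 3.2.1. It is met by a creatinine rise of more than three times baseline. It is also met by the high-baseline limb, "if baseline serum creatinine is greater than 4 mg/dl, then rise more than 0.5 mg/dl compared to baseline", or by the urine limb, "or urine output less than 0.3ml/Kg/hr for 24 hours; or anuria for 12 hours". The urine limb is restricted: "The above urine output criteria will be only used for patients who are in the ICU" with precise monitoring, while on the ward only creatinine counts. The reference value is a single one: "Baseline creatinine will be considered the creatinine upon admission prior to the index operation". Its timing relative to a dialysis session is not addressed.

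On data capture, Protocol X says "Participant Hb, creatinine, and troponin levels will be collected on days 1, 2, 3, 4, and 7 post-randomization" (or until discharge). For ICU patients it has anuria documented as evidence of ARF on the condition "If the patient has anuria for more than 12 hours", without reference to urine output before surgery. Protocol IX.C.2 extends the review of creatinine values to the 90-day visit.

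On eligibility, none of the 12 exclusion criteria in Protocol VII.B and SAP 4.2 concerns kidney disease. Protocol IX.C.1 collects "history of comorbidities, including coronary artery disease, end-stage renal disease, chronic obstructive pulmonary disease" among other conditions. SAP 4.4.1, SAP 6.5 and SAP Table 12 also carry end-stage renal disease as a baseline item.

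On adjudication, SAP 7.1 has a clinical events committee adjudicate every component of the primary endpoint. Protocol VI blinds the Endpoint Committee to allocation, and Protocol XVII.B includes a nephrologist among its members. Neither document gives the committee a rule for participants already on dialysis.

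**The concern.** The limb that requires a baseline creatinine above 4 mg/dl applies, by construction, mainly to people with advanced or end-stage kidney disease. For someone on chronic dialysis, one later value more than 0.5 mg/dl above the admission value is enough. No persistence is required and no new injury has to be shown. In the ICU, a participant who passed no urine before surgery meets the anuria criterion simply by remaining as before. Major amputation and bypass for peripheral arterial disease are core eligible operations, and end-stage renal disease is tabulated at baseline, so the case is foreseeable.

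Two things are at stake. The first is validity: the primary endpoint, the 30-day composite and the tertiary ARF analysis could each contain events that are not acute. If the committee instead sets such cases aside, it does so under a rule that is not written in either document. The second is dilution: events that occur equally in both arms for reasons unrelated to transfusion reduce both the absolute and the relative difference.

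**Working it through.** **Inputs.** From Protocol XVI.B and SAP 4.5: 30% restrictive, 22.5% liberal, two-sided 5%, 90% power, 1444 evaluable, 5% dropout, 1520 randomized. From Protocol II, Table 2: total ARF 11.1% at nadir Hb 6-9 gm/dl and 4.1% at 9-10 gm/dl. Assumed, because the documents give neither: f, the share on chronic dialysis, and q, the probability that such a participant meets the ARF rule without new injury, taken as equal in the two arms.

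**The plan's own figure.** With d = p1 - p2 and p̄ the mean of the two rates:

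n per arm = [1.960·√(2p̄(1-p̄)) + 1.2816·√(p1(1-p1) + p2(1-p2))]² / d²

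Here p̄ = 0.2625 and d = 0.075. The numerator is (1.960 × 0.6222 + 1.2816 × 0.6200)² = 4.057, and 4.057 / 0.005625 = 721.2, so 722 per arm or 1444 in total. Then 1444 / 0.95 = 1520. Both figures reproduce, and power at 722 per arm is 90.0%.

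**Dilution, if 30% and 22.5% are the rates without spurious events.** The observed rate in each arm is p + f·q·(1-p), so the difference is multiplied by (1 - f·q). Take f = 5%, q = 50%, so f·q = 0.025:

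- restrictive: 0.30 + 0.025 × 0.70 = 31.8%
- liberal: 0.225 + 0.025 × 0.775 = 24.4%
- difference: 7.5 × 0.975 = 7.3 points; relative reduction 23%
- power: Φ[(0.0731 × √722 - 1.960 × 0.6356) / 0.6335] = Φ(1.135) = 87.2%
- participants meeting the rule spuriously: 722 × 0.025 = 18 per arm

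| f | q | Restrictive | Liberal | Power at 722/arm | N for 90% |
|---|---|---|---|---|---|
| 0 | - | 30.0% | 22.5% | 90.0% | 1444 |
| 2% | 50% | 30.7% | 23.3% | 88.9% | 1500 |
| 5% | 50% | 31.8% | 24.4% | 87.2% | 1584 |
| 10% | 50% | 33.5% | 26.4% | 84.1% | 1734 |

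**Check against the protocol's data.** f·q is the spurious ARF rate that a scenario implies: 1%, 2.5% and 5% in the three rows. If the 38,153 eligible patients in Protocol II are split into the 25,343 with Hb 6-9 (Protocol XVI.A) and the remaining 12,810, taken as Hb 9-10, total ARF was (25,343 × 11.1% + 12,810 × 4.1%) / 38,153, or about 8.7%. The 10%/50% row already exceeds the whole Hb 9-10 rate. A scenario of 10% and 80% implies 8% spurious ARF, nearly all of the 8.7%. One of 15% and 100% implies 15%, above every observed total.

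**If the 30% already contains spurious events.** The database outcome was set to be the same as the trial's, and its ARF rule states no dialysis exclusion. With s = f·q, the genuine control rate is r0 = (0.30 - s)/(1 - s), the genuine liberal rate is l0 = 0.75·r0, and the observed liberal rate is l0 + s(1 - l0). At s = 0.025: r0 = 28.2%, l0 = 21.2%, observed liberal 23.1%.

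| f, q | Power, rule as written | Power with exception |
|---|---|---|
| 2%, 50% | 87.9% | 89.1% |
| 5%, 50% | 84.1% | 87.5% |
| 10%, 50% | 76.4% | 84.4% |

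In this case the exception recovers part of the loss but not the full 90%, because the control rate is then below 30%.

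**The two definitions side by side.** Protocol II(c) counts a creatinine above 4 mg/dl with a rise above 0.5. Protocol V.A and SAP 3.2.1 require the baseline itself to be above 4. The trial's limb is narrower overall, but aimed more squarely at people with chronic disease.

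**The case against.** The strongest reply is adjudication. A blinded committee that includes a nephrologist reviews every component, laboratory values are collected as supporting documents, ICU anuria is recorded as evidence and not scored automatically, and the component is labelled as acute injury. A sensible nephrologist may well set aside a chronic dialysis patient's creatinine. This stands as a reason to expect fewer spurious events. It does not close the gap, since the written definition counts such a case and no visible rule tells the committee otherwise. An operations manual or charter outside these documents may contain one.

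The second reply is about size. A reader might infer that dialysis participants meet the composite almost regardless of arm, and that power drops to about 80% (10% share, 80% meeting the rule) or 71% (15%, 100%). The documents do not support this. They give neither quantity. That creatinine routinely moves by more than 0.5 mg/dl between sessions is an assumption; if the admission value is a pre-dialysis peak, later values must exceed that peak. The anuria route is confined to the ICU. Those scenarios also fit poorly with the database ARF rates. That comparison has limits of its own: the database used creatinine ordered in routine care, had no urine output, and may have excluded end-stage renal disease without saying so.

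A reader might also infer that deaths and infarctions are hidden. They are not: each component is tested separately at 90 days, and one-year mortality is a secondary outcome.

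**Conclusion.** The gap is real and appears in both documents. The primary-endpoint rule, applied as written, can count a chronic state as an acute event in participants whom the plan admits and expects. The direction is dilution, provided that spurious events are equally likely in both arms. The magnitude cannot be established. For illustrative shares of 2% to 10% with half meeting the rule, and before any filtering by adjudication, the loss is about 1 to 6 points of power if the design rates are free of such events, and larger if the 30% already contains them. This should be fixed on grounds of endpoint validity. The power figures alone would not justify calling the design unsound.

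**What to change.** Before unblinding, state the following in Protocol V.A, SAP 3.2.1 and the adjudication instructions. Participants on chronic dialysis at baseline are not evaluable for the ARF component, remain in the ITT set, and are assessed on death, MI, coronary revascularization and stroke. Because the documents name end-stage renal disease and not dialysis, confirm dialysis status from the chart wherever that item is recorded.

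Apply the same rule to the 30-day composite, and restrict the denominator of the ARF rows in SAP Tables 22 and 23 accordingly. Add two sensitivity analyses of the primary endpoint: one under the rule as it now stands, and one excluding participants with baseline end-stage renal disease.

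Reconcile the 4 mg/dl condition between Protocol II(c) and Protocol V.A with SAP 3.2.1. Recheck the 30% control rate, since the database rule states no dialysis exclusion.

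The cost is a short amendment to a primary-endpoint component, a chart check in a subset, and two extra analyses. The composite rate will be slightly lower and the ARF denominator smaller.

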Objective 1: To examine the effect of transfusion strategies on a composite endpoint of all-cause post-randomization mortality, myocardial infarction (MI), coronary revascularization, acute renal failure, or post-randomization stroke in Veterans at high cardiac risk undergoing open surgical interventions

Hypothesis 1: A significantly smaller proportion of participants receiving blood under a liberal transfusion strategy will experience the composite compared to participants under restrictive transfusion strategy at 90 days after randomization.

B. Secondary Objectives

Objective 1: To examine the effect of transfusion strategies on post-randomization infectious complications.

Hypothesis 1: A smaller proportion of participants receiving blood under a liberal transfusion strategy will experience post-randomization infectious complications compared to participants under restrictive transfusion strategy at 90 days after randomization.

Objective 2: To examine the effect of transfusion strategies on post-randomization cardiac complications other than MI.

Hypothesis 2: A smaller proportion of participants receiving blood under a liberal transfusion strategy will experience post-randomization cardiac complications other than MI compared to participants under restrictive transfusion strategy at 90 days after randomization.

Objective 3: To examine the effect of transfusion strategies on all-cause mortality during the one year post-randomization follow-up.

Hypothesis 3: A smaller proportion of participants receiving blood under a liberal transfusion strategy will die from any cause compared to participants under restrictive transfusion strategy during one year follow-up after randomization.

Objective 4: To examine the effect of transfusion strategies on a composite endpoint of all-cause post-randomization mortality, MI, coronary revascularization, acute renal failure, or post-randomization stroke at 30 days after randomization.

Hypothesis 4: A smaller proportion of participants receiving blood under a liberal transfusion strategy will experience the composite endpoint compared to participants under restrictive transfusion strategy at 30 days after randomization.

Objective 5: To examine the effect of transfusion strategies on the length of hospital stay

Hypothesis 5: Liberal transfusion strategy will lead to a shorter length of hospital stay.

C. Tertiary Objective

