Pneumonia will be defined according to the CDC definition as chest radiograph or imaging with new or progressive infiltrate, consolidation, cavitation, or pleural effusion and any of the following: new onset of purulent sputum or change in character of sputum, or organism isolated from blood culture, trans-tracheal aspirate, bronchial brushings, or biopsy.

Sepsis will be defined as a combination of two of the following systemic inflammatory response syndrome (SIRS) criteria, **plus** suspected or present source of infection. SIRS criteria will

include the following: temperature greater than 38C, heart rate greater than 90 beats/min, WBC > 12,000 or < 4,000, or > 10% bands.

Outcome 2: A composite endpoint of cardiac complications (other than MI) at 90 days post-randomization: Cardiac complications will include new cardiac arrhythmias that necessitate new treatment, new or worsening congestive heart failure (CHF), and cardiac arrest not leading to death.

The diagnosis of cardiac arrhythmias will be based on EKG findings. Only arrhythmias that result in initiation of new treatment regimen (to include medications, implantable devices, or surgical intervention) during hospitalization will be recorded.

CHF will require at least one of the following symptoms or signs new or worsening: dyspnea at rest, orthopnea, or paroxysmal nocturnal dyspnea **and** radiological evidence of heart failure or worsening heart failure **and** increase/initiation of established treatment.

Cardiac arrest will be defined as the cessation of cardiac pump function activity that results in loss of consciousness and absence of circulating blood flow as evidenced by absent carotid pulse. Only episodes of cardiac arrest that are reversed will be collected under this endpoint. If they are not reversed the event will be categorized as death.

Outcome 3: All-cause mortality at 1 year after randomization.

We will determine vital status by telephoning participants after hospital discharge, by searching the electronic medical record and the VHA Death Ascertainment File (DAF).

Outcome 4: A composite endpoint of all-cause mortality, MI, coronary revascularization, acute renal failure, or post-randomization ischemic stroke at 30 days after randomization.

Outcome 5: Length of hospital stay.

C. Tertiary Outcomes

We will examine individual rates of the outcomes that consist of individual components of the primary endpoint.

VI. SUMMARY OF STUDY DESIGN

[figure not shown]

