Participants will be given an appointment for a clinic visit within one week after the 30 post-randomization day. Questions regarding symptoms related to MI, other cardiac events, stroke, pneumonia, and wound infection will be asked. If a participant has a readmission prior to the 30 day post-randomization time point, then the electronic medical record, will be reviewed to determine whether the reason for admission includes any of the complications that consist of the primary or other study endpoints, such as coronary revascularization or acute renal failure. If the participant has been admitted to a non-VA hospital, then complete records from this admission will be obtained from that hospital to document the reason for admission and whether any of the study endpoints have been developed which led to the readmission. The hospital records obtained will include History and Physical, all consultations, procedures, laboratory values, fluid cultures, copies of EKG and Echocardiography reports, as well as reports from all imaging studies performed, catheterization laboratory reports and operating room reports. To assure access to these records, release of information forms will have to be signed by the participant as part of the initial informed consent process. If the participant does not present for the follow up within two weeks from the anticipated appointment time, an electronic medical record review and phone call follow-up will be performed and focused questions will be asked, to identify the occurrence of any of the endpoints. Questions about interval readmission will also be asked at the follow up visit/call.

b) Ninety Day Follow-up

Participants will be given a clinic appointment within two weeks after the 90th post-randomization day. Questions regarding symptoms related to cardiac events, stroke, infectious complications will be asked as described above for the 30-day post-randomization follow up. If participants are unable to make the clinic visit within two weeks of the assigned appointment then an electronic medical record review and phone call follow-up will be performed as described above. Readmissions since previous follow-up will also be investigated with similar series of actions as with the 30 day post-randomization follow-up. Pertinent laboratory values (creatinine, troponin), EKG results, cardiac catheterization reports and operating room reports since the previous visit will be

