Outcome 4: A composite endpoint of all-cause mortality, MI, coronary revascularization, acute renal failure, or post-randomization stroke at 30 days after randomization.

Outcome 5: Length of hospital stay after randomization.

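### The arrhythmia part of the 90-day cardiac composite is recorded only if treatment starts in hospital, so its capture depends on in-hospital time, which is set after randomization

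*Protocol*

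**What the plan says.** Protocol V.B heads Outcome 2 as "A composite endpoint of cardiac complications (other than MI) at 90 days post-randomization" and lists its parts as "new cardiac arrhythmias that necessitate new treatment, new or worsening congestive heart failure (CHF), and cardiac arrest not leading to death". It then limits arrhythmia: "Only arrhythmias that result in initiation of new treatment regimen (to include medications, implantable devices, or surgical intervention) during hospitalization will be recorded". SAP 3.2.2 repeats that sentence unchanged. Heart failure has no limit by setting. For arrest the only restriction is "Only episodes of cardiac arrest that are reversed will be collected under this endpoint", which concerns survival of the episode and not where it happened.

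Protocol IV.B states two expectations that meet here. Hypothesis 2 is that a smaller proportion on liberal transfusion "will experience post-randomization cardiac complications other than MI compared to participants under restrictive transfusion strategy at 90 days after randomization". Hypothesis 5 is that "Liberal transfusion strategy will lead to a shorter length of hospital stay". The SAP counts the stay from randomization: "Length of hospital stay after randomization".

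After discharge, Protocol IX.C.2 says of the 90-day visit that "Questions regarding symptoms related to cardiac events, stroke, infectious complications will be asked", and Protocol VI has readmissions up to day 90 reviewed for the diagnoses in any endpoint. SAP 7.2 tests the composite as a simple proportion with a chi-square test at 0.01, and the Table 18 shell labels it a 90-day outcome.

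**The concern.** One component of three has its own, participant-specific window inside an endpoint reported as a 90-day rate. A participant still in hospital on day 20 who starts treatment for a new arrhythmia is an event. One who went home on day 5 and starts the same treatment in clinic on day 20 is not.

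The window is also not neutral between arms. Time in hospital is itself a secondary outcome that the trial expects transfusion strategy to change, and treating physicians know the allocation. If the liberal arm goes home sooner, it has less time in which an arrhythmia can be recorded, so a lower recorded rate can arise with no true difference. Blinded endpoint review does not help, because it cannot restore an event that was never recorded.

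The analysis offers no protection. SAP 7.2 and 7.4 adjust for age, RCRI and nadir Hb. They make no allowance for time in hospital and give no censoring rule for arrhythmia at discharge.

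**Working it through.** **Step 1. What is counted under each reading of the rule**

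| Event by day 90 | Index stay only | Index stay plus readmissions |
|---|---|---|
| Arrhythmia newly treated in the index stay | counted | counted |
| Arrhythmia newly treated in a readmission | lost | counted |
| Arrhythmia newly treated as an outpatient | lost | lost |
| Heart failure or reversed arrest, any setting | counted | counted |

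The third row is lost on either reading, so the mismatch with the 90-day label does not depend on how the ambiguity is resolved.

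**Step 2. Inputs for size**

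There is no plan figure for this outcome to reproduce. From the documents come 760 per group (Protocol XVI.B: 1444 / 0.95 = 1520, halved) and two-sided alpha 0.01 per secondary outcome. Everything else is assumed: equal true arrhythmia incidence in both arms, one fixed index stay per arm counted from randomization, recording that stops at discharge, and heart failure or arrest in 5% of each arm, independent of arrhythmia and observed to day 90.

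**Step 3. Formulas**

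- Front-loaded onset: recorded arrhythmia by discharge day L is F(L) = p × (1 − exp(−L/τ)) / (1 − exp(−90/τ)), where p is the true 90-day incidence. A very large τ gives uniform onset.
- Constant hazard h per day: F(L) = 1 − exp(−hL).
- Composite: 1 − 0.95 × (1 − F(L)).
- Chance of significance favouring liberal: Φ((d − 2.576 × se0) / se1), where d is the restrictive minus liberal rate, se0 the pooled and se1 the unpooled standard error at 760 per arm. With d = 0 this is 0.5%.

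**Step 4. One case in full** (p = 10%, τ = 10 days, stays 8 restrictive and 6 liberal)

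- Arrhythmia: 0.10 × 0.5507 / 0.9999 = 5.5% against 0.10 × 0.4512 / 0.9999 = 4.5%; ratio 0.82 with no true effect.
- Composite: 1 − 0.95 × 0.9449 = 10.2% against 1 − 0.95 × 0.9549 = 9.3%; ratio 0.91.
- d = 0.0095 and both standard errors are about 0.0152, so Φ((0.0095 − 0.0392) / 0.0152) = about 2.5%.
- With full 90-day capture both arms would read 1 − 0.95 × 0.90 = 14.5%. The rule loses 45% of restrictive-arm arrhythmias in this case (1 − 0.0551 / 0.10).

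**Step 5. Range**

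| Onset | True 90-day incidence | Stay R/L (days) | Arrhythmia recorded R vs L | Composite R vs L | Chance of spurious result |
|---|---|---|---|---|---|
| Uniform | 5% | 7/6 | 0.39% vs 0.33% | 5.4% vs 5.3% | 0.6% |
| τ = 30 | 10% | 8/6 | 2.5% vs 1.9% | 7.3% vs 6.8% | 1.5% |
| τ = 5 | 10% | 8/6 | 8.0% vs 7.0% | 12.6% vs 11.6% | 2.2% |
| τ = 10 | 15% | 10/7 | 9.5% vs 7.6% | 14.0% vs 12.2% | 6.5% |
| 0.5% per day | 36% | 8/7 | 3.9% vs 3.4% | 8.7% vs 8.3% | 1.2% |
| 1% per day | 59% | 7/5 | 6.8% vs 4.9% | 11.4% vs 9.6% | 7.5% |

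Changing the heart failure or arrest rate in the 15%, 10/7 case moves its 6.5% to 7.8% (at 3%) or 4.6% (at 10%). The overall range is about 1% to 8%.

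**The case against.** Several limits are real and stand.

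- A reader might infer that the whole composite is observed only for the length of the index stay. The documents do not support that. Two of the three components have no setting limit, hospitalization is not defined as the index stay, and Protocol VI has readmissions reviewed for all endpoints. If those count, the gap between arms shrinks.
- A reader might take the false-positive rate for arrhythmia alone, which at a constant 1% per day is about 11% for stays of 7 against 9 days and about 16% for 5 against 7. The plan never tests arrhythmia alone; the tertiary components are those of the primary endpoint. That hazard also implies 1 − exp(−0.9) = 59% with treated arrhythmia by day 90, and 0.5% per day implies 36%. Neither figure has any basis in the documents.
- The direction is conditional. Hypothesis 5 states no size and may fail. An arrhythmia can itself prolong the stay, which a fixed-stay model ignores.
- Requiring in-hospital treatment may be a deliberate severity filter. No such reason is given, and it would not justify the 90-day label.
- A reader might suppose that the existing day-90 record review can already supply the missing events. As written in Protocol IX.C.2 and SAP 4.4.2, its stated purpose covers revascularization, stroke, MI and renal failure only, and no protocol EKG is scheduled after discharge.

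What remains is that outpatient-treated arrhythmias are excluded on any reading, and that nothing in the analysis corrects for unequal time in hospital.

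**Conclusion.** The concern holds for the arrhythmia component of one of five secondary outcomes. The conflict between the 90-day definition and the in-hospital recording rule is plain from the text and needs no assumption. The bias towards Hypothesis 2 follows only if the liberal arm does spend less time in hospital.

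Its size cannot be derived from the documents. Under the assumptions shown, with index-stay recording, the chance of a spurious significant composite result favouring liberal is about 1% to 8% against 0.5% nominal. These figures illustrate the possible scale and are not estimates for this trial. The rule should be corrected, but it does not threaten the primary analysis.

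**What to change.** In Protocol V.B and SAP 3.2.2, count arrhythmias with EKG documentation and newly started treatment from randomization to day 90, whatever the setting. Collect them at the 30- and 90-day follow-ups, where cardiac symptoms are already asked about, and name arrhythmia explicitly in the day-90 record review.

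The protocol is at version 11, so data may already have been collected under the present rule. If those records cannot be completed:

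- state whether readmissions count as hospitalization;
- label the component as in-hospital and not as a 90-day event, in the text and in the table shells;
- add a sensitivity analysis of the composite, either without arrhythmia or with arrhythmia restricted to a fixed early post-randomization window common to both arms.

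The cost is more than a change of wording: an amendment, a revised instruction for the cardiac complications form, and chart and EKG retrieval for outpatient events. Outpatient capture will rely on EKGs obtained in ordinary care. The release of records described in Protocol VI covers hospital visits, so some non-VA outpatient tracings may be out of reach. Ascertainment would still be imperfect, but the definition would no longer depend on the day of discharge.
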